## 2.5 Data Management

### 2.5.1 Case Report Form Data

BioClinica (or designee) is responsible for creating the Electronic Data Capture (EDC) data entry screens, database and edit checks using definitions developed by Ionis. Ionis is responsible for the review, data management querying and locking of the database.

Data are single-entered into the EDC system by the investigator site staff. Programmed edit checks (computer logic that checks the validity of the data entered and also prompts for missing data that is expected to be entered) are run and automatic queries are generated. Ionis reviews all data for accuracy and validity and generates additional queries in the EDC system when necessary. The data is corrected or an explanation concerning the query is provided in the EDC system. After all data are entered, reviewed (by Data Management and Clinical Development) and queried, and all queries resolved, the database is locked.

### 2.5.2 Laboratory Data

#### 2.5.2.1 Bal/Bronchial Brushing

Bal cell counts and differentials will be analyzed by local labs and entered in the EDC system by the investigator site staff.

#### 2.5.2.2 Sputum Mucins (Total, MUC5AC, and MUC5B)

The sputum samples will be analyzed by PPD Development (PPD) for sputum mucins. Additionally, sputum from baseline and end of study will be sent to Spirovation for determination of cytokines and complement levels. Ionis, PPD, and Spirovation are responsible for the format of the safety laboratory electronic data transfers and the transfer schedule. The data results will not be stored in the EDC system. PPD, Spirovation, and Ionis are responsible for the review of the data. This process involves reviewing the patient and visit identifiers in the PPD data against the visit identifiers collected in the EDC system.

#### 2.5.2.3 Central Laboratory Data

The sites will collect the blood and urine samples and send to the central vendor, Medpace. Ionis and Medpace are responsible for the format of the safety laboratory electronic data transfers and the transfer schedule. Central laboratory data results will not be stored in the EDC system. Medpace and Ionis are responsible for the review of the clinical laboratory data. This process involves reviewing the patient and visit identifiers in the central laboratory data results data against the central lab data identifiers collected in the EDC system. Investigator sites have access to the data via lab reports sent directly from the laboratory or through the laboratory's web portal (in which case Investigators only have access to data from their site).

### 2.5.3 ECG Data

Ionis and ERT are responsible for the format of the cardiac safety and ECG data transfers and the transfer schedule. Cardiac safety and ECG data will not be stored in the EDC system.

Ionis and ERT are also responsible for the data reconciliation, which involves reviewing the patient and visit identifiers in the cardiac safety and ECG data against the visit identifiers collected in the EDC system.

#### **2.5.4 Spirometry, DLCO, and Plethysmography Data**

Ionis and ERT are responsible for the format of the spirometry, DLCO and plethysmography data transfers and the transfer schedule. The spirometry, DLCO and plethysmography data will not be stored in the EDC system. Ionis and ERT are also responsible for the data reconciliation, which involves reviewing the patient and visit identifiers in the spirometry, DLCO and plethysmography data against the visit identifiers collected in the EDC system.

#### **2.5.5 HRCT Data**

The sites will perform the computed tomography (CT) scans at both TLC and FRC and send the images to a central vendor, FLUIDDA. The outcome data will be generated by FLUIDDA. Ionis and FLUIDDA are responsible for the format of the data transfers and the transfer schedule. The data will not be stored in the EDC system. Ionis and ERT are also responsible for the data reconciliation, which involves reviewing the patient and visit identifiers in the cardiac safety and ECG data against the visit identifiers collected in the EDC system.

Since no patients have been enrolled in the HRCT subgroup at the time of treatment termination, the HRCT data are not collected.

#### **2.5.6 Diary and Questionnaire Data (E-RS, CAT, SGRQ)**

The diary and questionnaire data will be captured by ERT eCOA System. Patients will enter their assessments into the system using a tablet or other handheld devices. Ionis and ERT are responsible for the format of the electronic data transfers and the transfer schedule. The data will not be stored in the EDC system. Ionis and ERT are also responsible for the review of the data. This process involves reviewing the patient and visit identifiers in the questionnaire data against the data identifiers collected in the EDC system.

#### **2.5.7 Pharmacokinetics Data**

Ionis Pharmaceuticals, Inc. is responsible for the management and review of the plasma drug concentration data. Final data, which has been approved by Quality Assurance, will be stored in version-controlled repository

### **3 ANALYTICAL PLAN**

#### **3.1 General Overview of Analyses**

##### **3.1.1 Statistical Methods**

Descriptive summary statistics including number of subjects, mean, median, standard deviation, standard error, interquartile range (25th percentile, 75th percentile), and range

(minimum, maximum) for continuous variables, and counts and percentages for categorical variables will be used to summarize most data. All statistical tests will be conducted using 2-sided tests with 5% Type I error rate unless otherwise stated. As a Phase 2a study, adjustments for multiplicity of testing will generally not be used.

PK parameters will be summarized using number of Subjects, mean, standard deviation, coefficient of variation (CV), geometric mean, geometric %CV, median, minimum, and maximum.

### **General Presentation Considerations**

The minimum and maximum will be reported to the same number of decimal places as the raw data recorded in the database. The mean, median, lower quartile and upper quartile will be reported to one more decimal place than the raw data recorded in the database. The standard deviation will be reported to two more decimal places than the raw data recorded in the database. In general, the maximum number of decimal places reported shall be four for any summary statistic.

Categorical data will be summarized in terms of the number of subjects providing data at the relevant time point (n), frequency counts and percentages. Any planned collapsing of categories will be detailed in the text and the data displays.

Percentages will be presented to one decimal place and not be presented for zero counts. Percentages will be calculated using n as the denominator.

P-values greater than or equal to 0.0001, in general, will be presented to four decimal places. P-values less than 0.0001 will be presented as “<0.0001”.

Confidence intervals will be presented to one more decimal place than the raw data.

### **Baseline definition**

Baseline E-RS total and subscale scores are defined as the average of daily scores collected on Day 1 and within 6 days prior to Day 1.

Baseline liver chemistry parameters (ALT, AST, and total, direct and indirect bilirubin, alkaline phosphatase) are defined as the average of the non-missing values at Screening and Day 1 pre-dose, and any values in between.

Baseline ECG assessments are defined as the last triplicate prior to the first Study Drug administration. For numeric results, the baseline is the average of the triplicate. For character results, baseline is the worst result of the triplicate.

Baseline for other assessments is defined as the last non-missing measurement prior to the first Study Drug administration.

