## PROTOCOL SYNOPSIS (Continued)

Study Population (Continued)	Exclusion Criteria (Continued)
	

13. Acute upper or lower respiratory infection requiring antibiotics or antiviral medication within 4 weeks prior to enrolment (Visit 1)

14. Long term oxygen therapy (LTOT)

15. Patients participating in, or scheduled for, an intensive (active) COPD rehabilitation program (patients who are in the maintenance phase of a rehabilitation program are eligible to take part)

16. Recent history of, or current drug or alcohol abuse

17. Concomitant medication restrictions: Oral anticoagulants, oral steroids (e.g. prednisone or Medrol), theophylline, chronic azithromycin, or roflumilast

18. Have any other conditions, which, in the opinion of the Investigator would make the subject unsuitable for inclusion, or could interfere with the subject participating in or completing the Study

19. A positive PCR test for SARS-CoV-2 at any time prior to randomization

Treatment Groups	
Patients will be randomized 2:2:1:1 to treatment with:
 

• ION-827359 37.5 mg (1.5 mL) once per week

• ION-827359 75mg (3 mL) once per week

• Placebo (1.5 mL) once per week

• Placebo (3 mL) once per week

Study Drug Dosage and Administration	ION-827359 (25mg/mL) and placebo will be supplied in stoppered glass vials. A total of 1.5 mL or 3 mL will be placed into a Pari eFlow® nebulizer and administered by oral inhalation once weekly.
Study Visit Schedule and Procedures	
Blood and urine samples will be collected regularly throughout the study for safety, PK, and PD analyses. Appendix B shows a list of analytes required for the study. The safety of ION-827359 will be monitored in an ongoing fashion throughout the trial.
 
Screening and Baseline: Study Days -28 to -1
 
Laboratory and other study procedures will be performed to assess eligibility during the Screening Period. Patients will also receive a SARS-CoV-2 PCR test based on nasal/oral swab. Patients will be given an electronic diary to record their baseline daily symptoms starting on Day -7.

[figure not shown]

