## PROTOCOL SYNOPSIS (Continued)

Study Visit Schedule and Procedures (Continued)	
Treatment: Study Days 1 to 85
 
Eligible patients will be randomized 2:2:1:1 to ION-827359 (37.5 or 75 mg) or matching placebos. Patients will receive nebulized doses of Study Drug once weekly starting on Study Day 1. Both in-clinic and at-home dosing of ION-827359 will be performed. Patients will record their symptoms in a daily electronic diary and return for study visits to include monitoring and spirometry. There are 3 subset studies:
 

1. A subset of up to about 24 patients will have PK profile sampling performed after the first and last dose

2. A subset of up to about 60 patients will have low dose inspiratory and expiratory HRCT scans to assess regional lung ventilation performed before and post-treatment

3. A subset of up to about 18 patients will undergo bronchoscopy and BAL for target engagement and inflammatory biomarkers before and post-treatment

 
A patient may be enrolled in a maximum of 1 subset study
 
Post-Treatment: Study Days 86 to 162
 
Patients are to return to the Study Center for post-treatment visits on Study Days 92, 120 and 162.
 
Patients that discontinue treatment are encouraged to remain in the study for the Post-Treatment Evaluation Period and will conduct procedures outlined at Study Day 92 visit upon discontinuation of Study Drug.
 
Patients will continue their stable COPD medication regimen throughout the study (screening treatment and post-treatment periods).

Primary Endpoints	Change from Baseline to the primary time point (defined as the average of Weeks 13 and 14) in FEV 1 compared to placebo
Secondary Endpoints	

• Change from Baseline in the E-RS (evaluating respiratory symptoms) daily symptom diary to the primary time point

• Change from Baseline in the CAT to the Week 14 time point

• Change from Baseline in SGRQ to the Week 14 time point

• Change from Baseline in post-bronchodilator FEV1

• Pharmacokinetics

• Incidence and severity of treatment-emergent adverse events (TEAE)

• Abnormal findings in laboratory assessments, ECG, and vital signs

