SAP	Statistical Analysis Plan
SGRQ	St. George’s Respiratory Questionnaire
siRNA	small interfering ribonucleic acid
TLC	total lung capacity
Study Day 1	defined as the first day Study Drug product is administered to the patient
Study Drug	ION-827359 or placebo
SUSAR	suspected unexpected serious adverse reaction
TEAE	treatment-emergent adverse event
T max	time to maximal concentration
ULN	upper limit of normal
WBC	white blood cell
WOCBP	woman of child-bearing potential

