### **10.4. Definition of Baseline**

For all assessments, baseline will be defined as the last non-missing measurement prior to the first Study Drug administration, except for liver chemistry which is an average of the values at Screening and Day 1.

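### The SAP's E-RS baseline includes the Day 1 diary score without requiring that it precede the first dose (low priority)

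*Combined protocol and SAP*

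**What the plan says.** The Baseline definition in SAP Section 3.1.1 has the E-RS total and subscale baselines "defined as the average of daily scores collected on Day 1 and within 6 days prior to Day 1". It attaches no time of day and no order relative to dosing to the Day 1 score.

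The other entries in that list are all restricted:
- Liver chemistry uses the "average of the non-missing values at Screening and Day 1 pre-dose", plus any values in between.
- ECG uses "the last triplicate prior to the first Study Drug administration".
- All remaining assessments use the last available value before the first dose.

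Protocol Section 10.4 says that for all assessments "baseline will be defined as the last non-missing measurement prior to the first Study Drug administration". It excepts liver chemistry and nothing else.

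The protocol glossary says Study Day 1 is "defined as the first day Study Drug product is administered to the patient". Protocol Section 6.1.2 asks for one diary entry a day during run-in and treatment, without saying when in the day or whether before or after dosing. It also makes at least 4 entries in the 7 days before Day 1 a condition of randomization.

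SAP Section 3.3.2.1 summarizes change from baseline in the E-RS total and three subscales by treatment group. SAP Section 3.3 makes all efficacy analyses descriptive: 60 patients were randomized, 59 dosed, and 10 had completed Week 14 when treatment was terminated.

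**The concern.** A baseline should describe the patient before exposure. Taken literally, the E-RS rule lets a score recorded after the first inhalation count as baseline. If study drug changed symptoms acutely that day, part of the effect would be subtracted from every later change score for that patient. An acute worsening would raise baseline and make later change look better; an acute improvement would do the reverse.

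An acute effect is conceivable on the documents' own terms. Amendment 3 was written to guard against possible bronchospasm after inhalation, and the E-RS scores chest tightness and breathlessness. No document reports or quantifies such an effect on the diary.

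At stake is how the E-RS change summaries are read. No test or stated decision depends on them.

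**Working it through.** The plan gives no figure to reproduce here, so the check is on the windows and on the weight of the Day 1 entry.

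**Inputs.** E-RS baseline window and weekly EXACT windows: SAP 3.1.1. Four-entry minimum: protocol 6.1.2. Dosing days (1, 8, 15, … 85) and albuterol before each dose: protocol 6.1.3. Score range 0–40: SAP 3.3.2.1. The shifts s, d and c and the share f below are assumptions.

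**1. Windows.** The SAP baseline covers Days -6 to -1 and Day 1, seven days. The protocol's qualifying diary window is Days -7 to -1. A patient with the minimum 4 entries, one of them on Day -7, has 3 entries left in the SAP window before Day 1.

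**2. Weight of Day 1.** With n entries in Days -6 to -1, the weight is 1/(n+1).
- n = 6 (full diary): 1/7 = 0.143
- n = 4: 1/5 = 0.200
- n = 3 (minimum): 1/4 = 0.250

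**3. Effect on one patient.** If a post-dose Day 1 score carries an acute study-drug shift s, baseline moves by s/(n+1) and each change score by -s/(n+1).

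| Entries before Day 1 in window | s = 1 | s = 5 |
|---|---|---|
| 6 | 0.14 | 0.71 |
| 4 | 0.20 | 1.00 |
| 3 | 0.25 | 1.25 |

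Patients whose Day 1 entry is pre-dose or missing are unaffected.

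**4. Effect on the contrast with placebo.** Let f be the share of patients with a post-dose Day 1 entry (taken as equal across arms) and d the between-arm difference in mean acute shift among them. With full diaries, the difference in mean change moves by f × d / 7 in absolute value, relative to a pre-dose baseline.

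| f | d = 1 | d = 5 |
|---|---|---|
| 0.25 | 0.04 | 0.18 |
| 0.5 | 0.07 | 0.36 |
| 1 | 0.14 | 0.71 |

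At d = 0 it is zero.

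**5. Follow-up windows.** Week 2 is Days 2–8. The SAP formula, (Week-1)×7-5 to (Week-1)×7+1, gives Week 3 = Days 9–15, Week 13 = Days 79–85 and Week 14 = Days 86–92. Day 1 is in no post-baseline window. Weeks 2 to 13 each end on a nominal dosing day; Week 14 contains none.

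**6. A dosing-day effect common to all arms.** Let c be a shift present on every dosing day in every arm, as albuterol might cause. Assume full diaries, doses on nominal days and the same entry timing throughout.
- SAP rule, Weeks 2–13: c/7 - c/7 = 0.
- SAP rule, primary time point (mean of Weeks 13 and 14): (c/7 + 0)/2 - c/7 = c/14 - c/7 = -c/14.
- Day 1 post-dose entry excluded, Weeks 2–13: c/7 - 0 = +c/7.
- Day 1 post-dose entry excluded, primary time point: +c/14.

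So for a common effect the SAP rule is better in Weeks 2–13 and equal in size, with opposite sign, at the primary time point.

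**The case against.** The best defence is that including Day 1 looks deliberate. The baseline window is the weekly grid moved one step back, each window through Week 13 ends on a dosing day, and Day 1 is not used twice. Protocol Section 4.2 and SAP Section 2.2 place randomization after all Baseline assessments, which points to a pre-dose intent. This explains why Day 1 is in the window. It does not supply the missing condition: neither passage names the diary or restricts which Day 1 score may be used.

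Three stronger readings are tempting, and the documents do not support them.

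- A reader might infer that albuterol, given before study drug, is itself a reason to change the rule. Step 6 of the working shows otherwise: an effect common to all arms cancels in Weeks 2–13 under the SAP rule and is no smaller at the primary time point under the alternative.
- A reader might infer that the window contradicts the synopsis, where "Patients will be given an electronic diary to record their baseline daily symptoms starting on Day -7" stands under "Screening and Baseline: Study Days -28 to -1" while the diary reappears under Treatment. That is weak. The run-in visit is 7 ± 1 days before randomization, so a compliant patient may have no Day -7 entry. Other baselines are also taken on Day 1 although the synopsis lists it under Treatment.
- A reader might infer that post-dose scores did enter baseline. Nothing in the documents shows this.

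It is also fair to object that s, d and f have no source in the documents, and that the SAP plans no model-based contrast. Both points stand and limit the weight of the finding. The conflict with protocol Section 10.4 remains.

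**Conclusion.** The point holds in a narrow form. The E-RS rule, alone among the SAP's baseline definitions, admits a post-dose value, and it does so against the protocol's own requirement. The weight at issue is 1/7 of baseline with a full diary and at most 1/4. For an assumed acute study-drug shift of 1 to 5 points, a patient's change scores move by 0.14 to 1.25 points. With full diaries the contrast with placebo moves by f × d / 7, which is nil unless the acute effect differs between arms. Whether any Day 1 entry was made after dosing, and whether study drug has an acute effect on the E-RS, cannot be determined from the documents.

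Priority is low: the endpoint is secondary, the summaries are descriptive, and few patients reached Week 14. Confidence in the reading of the text is good; the size of any effect is unknown.

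**What to change.** Add one sentence to the Baseline definition in SAP Section 3.1.1: the Day 1 entry counts toward the E-RS baseline, total and subscales, only if it was completed before the first dose; if entry times are unavailable, average only the entries before Day 1.

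**Cost.** At most one diary day is lost per patient. A patient at the protocol minimum would keep 3 entries in the present window. The pre-dose condition needs diary entry times, and SAP Section 2.5.6 does not say whether these are captured or transferred; the fallback does not need them.

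**Trade-off.** A dosing-day effect common to all arms would no longer cancel in the within-group changes for Weeks 2–13. Under the assumptions of step 6 it would add c/7 to those changes, or 0.14 points for c = 1. It would not affect the contrast with placebo.

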## PROTOCOL AMENDMENT

**Protocol Number:** ION-827359-CS2**Protocol Title:** A Double-Blind, Placebo-Controlled, Phase 2a Study to Assess the Safety, Tolerability, and Efficacy of ION-827359 in Patients with Mild to Moderate COPD with Chronic Bronchitis**Amendment Number:** 3**Amendment Date:** 2 February 2021

The major purpose of this amendment is to help prevent any potential bronchospasm after inhalation of Study Drug.

A list of changes to the protocol are below:

Protocol Section	Description of Change	Rationale
Section 6.1.3 Treatment Period	
The following is deleted from Table 1 (Withhold times for bronchodilators):
 
LABA (e.g., formoterol or salmeterol) 24 hours Ultra-LABA (e.g., indacaterol, vilanterol, or olodaterol) 36 hours LAMA (e.g., tiotropium, umeclidinium, aclidinium, or glycopyrronium) 36 – 48 hours
 
The following is added:
 
The usual dose of bronchodilators should not be taken the morning of the visit, until after spirometry is performed and prior to dosing (if applicable) with the study medication. Albuterol (salbutamol) 2 puffs, should be dosed prior to study drug both for in-clinic and at-home dosing.
	To help prevent any potential bronchospasm
Appendix A Schedule of Procedures	
Footnote 2 (vital signs) currently reads:
 
 BP, heart rate (HR), respiratory rate (RR), temperature
 
Will be amended to:
 
 BP, heart rate (HR), respiratory rate (RR), temperature, and pulse oximetry
	Correct an omission.
Appendix A Schedule of Procedures	
Footnote g added for spirometry on Day 1:
 
Perform spirometry (pre-Study Drug) pre and 20-30 minutes post albuterol dose (2 puffs) and then perform spirometry 1 and 2 hours post-Study Drug dosing.
	Collect baseline post-albuterol spirometry

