#### 6.1.3. Treatment Period

Eligible patients will be administered Study Drug (ION-827359 or placebo) on a weekly basis for a total of 13 doses. These doses will be administered in the clinic on Days 1, 15, 29, 43, 57, and 85. Doses on Days 8, 22, 36, 50, 64, 71, and 78 will be self-administered by the patient at home. Safety and clinical laboratory evaluations will be performed periodically throughout the Treatment Period (Appendix A, Appendix B and Appendix C). A subset of about 24 patients will undergo additional blood sampling for PK analysis after dosing on Day 1 and Day 85. The subset of patients undergoing HRCT scans will have a follow-up scan performed on Day 92.

Any AEs and concomitant medications will be recorded. All safety data including AEs, BP, and concomitant medications will be reviewed by the Sponsor's Medical Monitor or designee on an ongoing basis throughout the trial.

Prior to each visit (after Screening) the patient's bronchodilators should be withheld as follows:

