## **8.3. Protocol-Required Treatment Procedures**

### **8.3.1. Spirometry**

Spirometry assessments will be made in accordance with ATS/ERS guidelines ([Graham et al. 2019](#)). At all time points, 3 technically acceptable measurements should be made and recorded. Spirometry assessments may be performed up to 8 times to obtain 3 acceptable readings according to ATS guidelines ([Graham et al. 2019](#)). The highest FEV1 and FVC readings from each assessment will be used for analysis even if the FEV1 and FVC values come from 2 different forced exhalations. The baseline values are those performed immediately (within 30 minutes) prior to inhalation of study medication. The reference values will be that of GLI 2012. Spirometry will be performed by a central vendor who will perform quality control on spirometry efforts.

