### **10.3. Populations**

Full Analysis Set (FAS): all randomized patients who received at least 1 dose of Study Drug (ION-827359 or placebo) and who have at least 1 post-Baseline efficacy assessment (i.e., post-Baseline FEV1 assessment, E-RS score, CAT score, SGRQ-C score, or post-bronchodilator FEV1 assessment).

Per Protocol Set (PPS): a subset of FAS who have received at least 9 doses of Study Drug and have no significant protocol deviations that would be expected to affect efficacy assessments.

Safety Set: All patients who are randomized and receive at least 1 dose of Study Drug.

PK Population: All patients who are randomized and receive at least 1 dose of Study Drug.

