### **Time (time is in reference to Study Drug (ION-827359 or placebo) administration):**

a Pre-dose

b Pre- and 20-30 minutes post-albuterol dose

c Pre-dose, and 2 hour

d Pre-dose, 1, and 2 hour

e For the subset of patients with full PK sampling; Pre-dose, 0.5, 1, 1.5, 2, 3, 4, 6, 8,12, 24 hours post-inhalation (window of  $\pm$  10% of the timepoint in minutes)

f In the morning, prior to study visit

g Perform spirometry (pre-Study Drug) pre and 20-30 minutes post albuterol dose (2 puffs) and then perform spirometry 1 and 2 hours post-Study Drug dosing.

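### No SAP rule says whether baseline FEV1 is the Day 1 reading before or after albuterol (read literally, it is the one after); Week 13 and the >20% reference are also unlabelled

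*Combined protocol and SAP*

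**What the plan says.** **Baseline.** SAP 3.1.1 gives E-RS, liver chemistry and ECG their own baseline rules. Spirometry falls under the remainder: "Baseline for other assessments is defined as the last non-missing measurement prior to the first Study Drug administration". Protocol 10.4 agrees: "baseline will be defined as the last non-missing measurement prior to the first Study Drug administration". Protocol 8.3.1 adds, for spirometry, "The baseline values are those performed immediately (within 30 minutes) prior to inhalation of study medication".

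**Day 1 sessions.** Appendix A footnote g, added by Amendment 3, reads "Perform spirometry (pre-Study Drug) pre and 20-30 minutes post albuterol dose (2 puffs"), followed by sessions 1 and 2 hours after Study Drug. The amendment's reason is "Collect baseline post-albuterol spirometry".

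**Follow-up readings.** Protocol 6.1.3 states "Prior to each visit (after Screening) the patient's bronchodilators should be withheld as follows". It also holds back the usual bronchodilators until spirometry is done, and has 2 puffs of albuterol given before each Study Drug dose.

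**Week 13.** Footnote b schedules a session before and a session after albuterol. The SAP window table has one Week 13 spirometry row (Days 72 to 88), although the 1- and 2-hour readings on Day 1 and at Week 9 have rows of their own.

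**Post-bronchodilator FEV1.** Protocol 10.3 counts it apart from FEV1 in the FAS definition ("CAT score, SGRQ-C score, or post-bronchodilator FEV"), and SAP 3.3.2.4 summarises it separately but gives it no baseline definition.

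**Falls above 20%.** SAP 3.3.1 tabulates patients and doses with such a fall and names no reference reading.

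**The concern.** A change from baseline is interpretable only if both readings are of the same kind. A post-albuterol baseline set against pre-albuterol follow-up takes the albuterol response out of every affected patient's change. SAP 3.3 reports by-arm descriptive changes only, so a reader sees the within-arm means, where such a shift does not cancel.

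The table of falls above 20% bears on bronchospasm after inhalation, which Amendment 3 was written to prevent. Its counts depend on which reading is the reference. As written, two competent programmers could produce different tables from the same data.

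**Working it through.** **1. The plan's own figure.** Inputs from SAP 3.1.3: difference 100 mL, SD 220 mL, 116 active against 58 placebo, two-sided 5%. SE = 220 x sqrt(1/116 + 1/58) = 35.4 mL; 100/35.4 = 2.83; power = Phi(2.83 - 1.96) = 80.7%. The stated power of at least 80% reproduces. This point does not touch it; the 100 mL serves below only as a yardstick.

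**2. Which Day 1 reading the rule selects.** The order is pre-albuterol session, albuterol, a wait of 20-30 minutes, post-albuterol session, Study Drug. The last measurement before Study Drug is the post-albuterol one.

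**3. Whether protocol 8.3.1 rescues the earlier reading.** It allows 30 minutes before inhalation. After the wait, 30 - 20 = 10 minutes at most and 30 - 30 = 0 at least remain for the second session and the start of dosing. The same section says "Spirometry assessments may be performed up to 8 times to obtain 3 acceptable readings". The pre-albuterol reading will often fall outside the limit, so 8.3.1 does not secure it.

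**4. Size if the literal rule is applied.** Shift in an arm's mean change = -(share of patients with a Day 1 post-albuterol reading) x (mean albuterol response R). Neither input is in the documents. Assume R = 50-150 mL:

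| Share affected | Shift in by-arm mean change |
|---|---|
| 10% | -5 to -15 mL |
| 25% | -12.5 to -37.5 mL |
| 50% | -25 to -75 mL |
| Series kept separate | 0 |

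Randomisation makes share and R equal across arms in expectation, so the expected active-placebo difference is unchanged. A chance 10-point difference in share between arms would be worth 5-15 mL.

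**5. Where the shift would appear.** Treatment stopped on 29 April 2021 (SAP 1.1). A Day 85 dosing visit by then needs Day 1 by 29 April - 84 days = 4 February, or 6 February with the 2-day window. Amendment 3 is dated 2 February, and protocol 12.1 requires approvals before use. So almost every patient with a scheduled Week 13 visit started without the Day 1 post-albuterol session, and the baseline choice matters little for them. Later starters can enter the Week 13 or 14 windows through an early-termination visit, but the documents give no count. The shift therefore falls mainly on early visits and the end-of-treatment summary.

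**6. Week 13 label.** Two sessions share one window row. The intended value for the primary time point is most naturally the pre-albuterol one, but this is not stated.

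**7. Falls above 20%.** Day 1 offers two pre-dose references. At Week 9 under Amendment 3 the pre-dose reading precedes albuterol and the 1- and 2-hour readings follow it. With pre-albuterol level F and response r, a fall to 0.8F is a fall of 1 - 0.8F/(F + r) from the post-albuterol level. Both inputs are assumptions:

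| F | r = 0.05 L | r = 0.15 L |
|---|---|---|
| 1.2 L | 23.2% | 28.9% |
| 1.8 L | 22.2% | 26.2% |
| 2.4 L | 21.6% | 24.7% |

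A pre-albuterol reference thus counts a post-dose fall only when it exceeds about 22-29% of the post-albuterol level.

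**8. Post-bronchodilator series.** Its last pre-dose reading is the 4-puff Screening session (protocol 6.1.1) for patients who started before Amendment 3, and the 2-puff Day 1 session afterwards. Footnote b gives no puff count for Week 13. By the dates in step 5, nearly all scheduled Week 13 readings would be compared with the 4-puff Screening value.

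**The case against.** The best defence is that the documents treat FEV1 and post-bronchodilator FEV1 as separate assessments (protocol 10.3 and 10.6.3.2, SAP 3.3.2.4). Applied to each in turn, the baseline rule gives the pre-albuterol value for the first and the post-albuterol value for the second. The amendment's rationale and the withholding rule, which also covers Day 1, point the same way. This stands as evidence of intent. It does not supply a rule: nothing in SAP 3.1.1 says that the baseline or the window table is to be applied by session type.

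A reader might also infer that the primary time point could move substantially, in either direction, because SAP 3.3.1 takes the best reading and SAP 3.1.1 averages ties. The documents do not support that. The best reading follows directly on the three acceptable efforts and, with protocol 8.3.1, most naturally means the best effort within a session. The averaging rule concerns two equally near visits, not two sessions at one visit. The dates above leave few patients with both a scheduled Week 13 visit and a Day 1 post-albuterol reading.

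On falls above 20%, counting doses that led to a fall suggests a same-day comparison, and Week 9 then has a single pre-dose candidate. That narrows the ambiguity mainly to Day 1. The Week 9 reference would still be a pre-albuterol reading set against post-albuterol ones. SAP wording cannot change that order, but it can disclose it.

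**Conclusion.** The gap is real and minor. Read literally, the baseline rule selects the Day 1 post-albuterol FEV1 for patients treated under Amendment 3, against the apparent intent. If programmed that way, by-arm mean changes fall by 5-15 mL per 10 percentage points of affected patients, at an assumed response of 50-150 mL. The share is unknown, and the shift is zero if the series are kept apart.

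A reader might infer a biased treatment comparison. None follows: the expected active-placebo difference is unchanged, and SAP 3.3 contains no efficacy test to affect. No range or sign should be claimed for the primary time point. The missing reference for falls above 20% holds on Day 1. At Week 9 the mixed albuterol status can under-count post-dose falls.

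**What to change.** - In SAP 3.1.1, define baseline FEV1 as the last pre-albuterol reading before first dose, and reconcile this with protocol 8.3.1 and 10.4.
- Label the Week 13 spirometry row by session, and use the pre-albuterol value for the primary time point.
- Treat post-bronchodilator FEV1 as its own series with its own baseline, and flag patients who have only the 4-puff Screening reading.
- In SAP 3.3.1, name the reference reading for falls above 20% on Day 1 and at Week 9, and state that Week 9 post-dose readings under Amendment 3 follow albuterol.
- Reconcile the passages on albuterol puff counts (protocol 6.1.1, footnotes b and g). This point takes no position on which count is right.

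The cost is a few lines of SAP wording and a programming flag on readings already collected. No new data are needed, and sample size and power are untouched.
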